8.2 Primary Safety Endpoint

The primary safety endpoint is a major adverse event rate at 30 days defined as: device malfunction, Grade III Szilagyi Infection or any cause mortality.

Device malfunction-	Any case in which the device does not perform in its intended function when used in accordance with the instructions for use. All device malfunctions will be reported to the sponsor. Malfunctions that result in an adverse event must be reported as so. Malfunctions that do not result in an adverse event do not need to be recorded as an adverse event as they are not considered an adverse event. The malfunctioned device will be returned to Acelity.
All-Cause Mortality-	Death from any cause related or unrelated to surgery, use of Prevena or Dermabond. Any death will be reported to the Sponsor as soon as possible A written report of the death will be provided to the sponsor within 10 business days and will be provided to the IRB per guidelines. If requested, a copy of the death certificate and autopsy results be sent to the sponsor when available. Any other source documents related to the death should also be provided to the sponsor. If no source documents are available, the PI is submit a letter to the sponsor describing the circumstances of the subject's death.
Groin incision infection	Szilagyi Grade III infection of the randomized groin incision.

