Clinical Protocol

NCT#02836990

Revised: August 11, 2017

Prevena Incision Management System Versus Dermabond in the Prevention of
Groin Wound Infections in Patients Undergoing Vascular Surgery

Principal Investigator: [name]
Department of Surgery
Buffalo General Medical Center
[contact]
[contact]

Sponsor: Acelity

Clinical Protocol Acceptance

I have read this protocol and agree to adhere to the requirements. I will provide copies of this protocol and all pertinent information to the study personnel. I will discuss this material with them and ensure that they are fully informed regarding the conduct of this study, other applicable regulations, to applicable laws and the University of Buffalo Health Science Institutional Review Board (HSIRB) requirements.

Principal Investigator Signature

____/____/____
DD MM YY

Principal Investigator Printed Name

Investigational Site

Protocol Synopsis

Prevena versus Dermabond in the Prevention of Groin Wound Infections in Patients Undergoing Vascular Surgery	
Protocol Number	
Test Device	Prevena Incision Management System
Primary Objective	To evaluate the clinical efficacy and cost effectiveness of Prevena versus Dermabond in preventing groin wound infections in patients who undergo vascular surgery requiring a groin incision.
Study Design	A prospective randomized study comparing groin wound infection rates and costs of hospitalization for Prevena and Dermabond in patients who undergo vascular surgery which requires a groin incision
Eligibility Criteria	Adults 18-85 who are scheduled to undergo vascular surgery which requires a groin incision who are able to consent and are willing to comply with follow-up and are or have a responsible individual deemed able to take care of a wound.
Number of Subjects	140 patients: 70 in each arm of the study
Number of Sites	Buffalo Medical Center, Kaleida Health
Follow-up schedule	Clinical follow-up will be daily throughout hospitalization including day of discharge and within 30 days of surgery to evaluate healing of the groin incision.
Primary Safety Endpoint	Major adverse event rate at 30 days defined as: groin wound infection
Primary Effectiveness Endpoint	30 day healing of the groin wound

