9.2 Research Procedures

- Baseline Requirements
 - Informed consent must be obtained from the subject prior to enrollment. The following is a list of all assessments and tests that are required during the baseline period. Assessment is based on data available to the investigator at time of enrollment.
 - Medical History- It is required that the subject's clinical history and pre-existing conditions be assessed and documented
 - Physical Exam- It is required that the subject undergo a pertinent arterial and venous physical exam and the results be documented
 - Concomitant Medication use- It is required that the subject's use of medications related to the study be provided and documented at baseline and throughout follow-up. Concomitant use includes antibiotics, NSAIDs, steroids, aspirin, anticoagulants and antiplatelet medications
 - Laboratory Testing- Routine laboratory testing performed prior to a surgical procedure will be documented: CBC without Differential, Electrolyte Panel
- Procedure Requirements
 - Concomitant Medication Use
 - Adverse Event (AE) evaluation- any undesirable medical occurrences in a subject related or unrelated to the study device, study procedure or study requirements that is identified or worsens during the clinical study. Adverse events must be assessed and documented by the investigator at the time of the procedure and at all follow-

ups (scheduled and unscheduled visits). All suspected AEs must be recorded and reported to the sponsor. See 12.0 **Data Safety Monitoring** for definitions of specific AEs and AE categorization.

- Post Procedure Requirements
 - Clinical Status Evaluation :
 - Sizalgyi Infection Score
 - Grade 0- No Infection
 - Grade I- Dermis only
 - Grade II- Subcutaneous tissue involvement
 - Grade III- Arterial Graft Involved
 - Lower extremity vascular assessment
 - Documentation of pulses, color, movement
 - Sensation, Ankle Brachial Index (ABI)
 - Concomitant Medical Use: Prophylactic antibiotics will be noted. Use of additional antibiotics along with indication will be recorded. Other medications such as NSAIDs, steroids, aspirin, anticoagulants and antiplatelet medications will also be recorded.

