11.4 Quality Control of Collected Data – 11.11 Handling and Transmission of Data

All appropriate sections of the case report form (CRF): (See appendix) will be completed by the coordinator, viewed and signed by the principal investigator and entered into the database within two weeks following the subject's discharge for the index procedure. The follow-up forms will be completed within a timely fashion after follow-up.

Study monitors designated by the sponsor will review the information documented in the CRF to verify that the recorded information is consistent with the medical record or other source documents and that input of this information into the data base is accurate. Errors or incomplete data will be rectified. All information will be treated as confidential. The following individuals will have full access to the data: Principal investigator, clinical

coordinator, statistician Co-investigators, vascular technicians, Core Lab personnel and study monitors will have access on an as needed basis.

Table 2. Adverse Event Definitions and Categorizations

Adverse Event	Any undesirable medical occurrences in a subject whether or not it is related to the study device, procedure or study requirements that is identified or worsens during the clinical study	
Major Adverse Event	A primary safety endpoint adverse event defined as Szilagyi Grade III infection of the randomized incision and all-cause mortality	Grade III Szilagyi infection of the randomized incision All-cause mortality
Serious Adverse Event	Any adverse event that results in death, is life threatening, requires > 24 hour in-patient hospitalization, or prolongation of an existing hospitalization, requires intervention to prevent permanent impairment/damage or results in persistent or significant disability/incapacity	Myocardial Infarction Congestive Heart Failure Pulmonary Embolus Respiratory Failure Stroke Cardio/Pulmonary Arrest Thirty day hospital readmission for Grade II or III Szilagyi infection of the randomized incision
Unanticipated Adverse Event	Any serious adverse event leading to injury, illness or death of a subject not previously identified in nature, severity or degree of incidence in this protocol, literature or application (including a supplementary plan or application) that may be directly related to use of the device	

Table 3. Procedure Related Categories for Adverse Events

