Procedure Related Adverse Event	AE that have a strong temporal relationship to the procedure and an alternative etiology is unlikely
Probably Procedure Related Adverse Event	AE that have a strong temporal relationship to the procedure and an alternative etiology is less likely than the potential relationship to the procedure
Probably–Not Procedure Related Adverse Event	AE that have minimal or no temporal relationship to the procedure and/or a more than likely alternative etiology
Not Procedure –Related Adverse Event	AE is due to the underlying disease state or concomitant medication or therapy and not caused by the procedure

Criteria for MAE and SAE

Serious Infection-	Grade III Sziglgyi infection of the randomized incision
Myocardial Infarction-	Per the ESC/ACC definition for acute, evolving or recent MI Typical rise and gradual fall of Troponin or more rapid rise and fall of (CK-MB) biomarkers or myocardial necrosis with at least one of the following: 
 • Ischemic symptoms • Development of pathologic Q wave on ECG • ECG changes indicative of ischemia (ST segment elevation or depression) or coronary artery intervention (ie: coronary angioplasty • Pathologic findings of an acute MI
Congestive Heart Failure-	New or worsening shortness of breath confirmed by chest x-ray findings consistent with CHF and/or requiring unscheduled dialysis or fluid restriction
Cerebrovascular Accident-	A neurologic deficit lasting more than 24 hours, or lasting less than 24 hours with a brain imaging study showing infarction.
Pulmonary Embolus-	Embolus in the pulmonary vascular documented by CT findings
Respiratory Failure-	Respiratory difficult requiring intubation
Cardio-Pulmonary Arrest-	Loss of pulse and respiration. Need for cardio-pulmonary resuscitation to prevent impending death

Interim analysis will be performed of the primary and secondary endpoints after half of the subjects are enrolled and again when all subjects are enrolled. Anova will be used to determine differences in infection rates between the two treatment arms. The PI will verbally communicate the findings to Acelyty with recommendations to continue, stop the study or make changes to the protocol if additional patients are needed to achieve statistical significance. These will be provided in writing within 4 weeks.

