32.0 Definitions

Adverse Event Definitions

Adverse Event	Any undesirable medical occurrences in a subject whether or not it is related to the study device, procedure or study requirements that is identified or worsens during the clinical study
Major Adverse Event	A primary safety endpoint adverse event defined as thrombosis of the AV fistula, fistula re-intervention and all-cause mortality
Serious Adverse Event	Any adverse event that results in death, is life threatening, requires > 24 hour in-patient hospitalization, or prolongation of an existing hospitalization, requires intervention to prevent permanent impairment/damage or results in persistent or significant disability/incapacity
Unanticipated Adverse Event	Any serious adverse event leading to injury, illness or death of a subject not previously identified in nature, severity or degree of incidence in this protocol, literature or application (including a supplementary plan or application) that may be directly related to use of the device

Allergic Reaction: Allergic reaction which could result in nausea, rash, wheezing, edema induced thrombotic events, urticarial or shock.

Aneurysm: A localized, pathologic, blood filled dilation of a blood vessel caused by weakening in the vessel wall.

Artery Perforation: Extravasation of a small quantity of blood outside the arterial adventitial layer.

Artery Rupture: Large transmural disruption of a vessel with gross extravasation and hemorrhage.

As-Treated Analysis: An “As Treated” analysis is one in which all participants in a study are analyzed according to the treatment received , regardless of the initial assignment and regardless of the amount of follow-up.

Bleeding: Blood loss resulting from surgery that may require transfusion of blood products.

Cardio-Pulmonary Arrest: Loss of pulse and respiration. Need for cardio-pulmonary resuscitation to prevent impending death

Concomitant Medication: Medication use related to the study, including antibiotics aspirin, NSAIDs, steroids.

Congestive Heart Failure:

Acute: New or worsening shortness of breath confirmed by chest x-ray findings consistent with CHF and/or requiring unscheduled dialysis or fluid restriction.

Established or History of CHF: New York State Heart Failure Classification

Class	Description
Class I	No physical limitations and is Asymptomatic
Class II	Mild symptoms while doing light exercise or activities of daily living
Class III	Difficulty doing simple activities of daily living

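### The primary safety endpoint (30-day major adverse event rate) is defined inconsistently across the synopsis, Section 8.2, Table 2 and Section 32.0, and nothing visible says which definition governs

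*Combined protocol and SAP*

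**What the plan says.** Four places define the 30-day major adverse event (MAE), and all four tie it to the primary safety endpoint.

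- **Protocol Synopsis, primary safety endpoint row:** "Major adverse event rate at 30 days defined as: groin wound infection". No grade is given, and neither death nor malfunction is mentioned.
- **Section 8.2:** "The primary safety endpoint is a major adverse event rate at 30 days defined as: device malfunction, Grade III Szilagyi Infection or any cause mortality". A row beneath it, for groin incision infection, specifies Grade III at the randomized groin.
- **Table 2 (adverse event definitions):** "A primary safety endpoint adverse event defined as Szilagyi Grade III infection of the randomized incision and all-cause mortality". Malfunction is absent.
- **Section 32.0:** "A primary safety endpoint adverse event defined as thrombosis of the AV fistula, fistula re-intervention and all-cause mortality". Infection is absent.

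Section 8.2 adds two rules on malfunction: "All device malfunctions will be reported to the sponsor", and "Malfunctions that do not result in an adverse event do not need to be recorded as an adverse event". Section 32.0 defines device malfunction for the Prevena system only.

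The analysis plan (Section 9.12, repeated in Section 11) covers the ordinal Szilagyi grade and cost. It gives no analysis of the safety endpoint. The interim paragraph that follows the MAE and SAE criteria names only infection rates as the quantity to be compared.

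**The concern.** A primary safety rate needs one rule for which patients count. Here a patient with a Grade I infection, a patient who dies without infection, and a Prevena patient whose device fails could each be counted or not, depending on the page the analyst follows. With no analysis section for safety, nothing later in the document settles the choice.

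Malfunction needs separate attention. Section 8.2 places it in the rate, yet says that a malfunction causing no adverse event is not an adverse event. It therefore leaves open whether a harmless malfunction is a *major* adverse event. On the Section 32.0 definition only one arm can score this component. Unless the rule is explicit, a reader of the final rates could not tell a difference in patient harm from a count of Prevena device failures.

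Leaving the choice open until results are known would also allow the definition to be picked with the results in view.

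**Working it through.** **Step 1: compare the definitions.**

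| Component | Synopsis | 8.2 | Table 2 | 32.0 |
|---|---|---|---|---|
| Infection | yes, grade not stated | Grade III | Grade III | no |
| Death, any cause | no | yes | yes | yes |
| Device malfunction | no | yes | no | no |
| AV-fistula events | no | no | no | yes |

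No two columns agree. Section 8.2 joins its components with *or* and Table 2 with *and*. The table layout suggests that either event suffices, but the wording differs.

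**Step 2: look for a rule of precedence.** None is visible. Section 9.2 sends the reader to a Section 12.0 "for definitions of specific AEs and AE categorization". That concerns adverse event definitions and does not rank the endpoint definitions. The 12.0 heading may simply have been lost when the PDF was read, so nothing rests on its absence.

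**Step 3: check the planning inputs.** The plan states no figure for safety. The only usable inputs are the grade probabilities in Section 9.13 (none, I, II, III): Prevena 0.90, 0.08, 0.019, 0.001; Dermabond 0.70, 0.16, 0.11, 0.03; 70 per arm. Simulating the ordinal efficacy comparison from these gives power 0.884 (score test, 10,000 runs) and 0.889 (likelihood-ratio test, 3,000 runs), against the stated 0.88. The inputs are therefore read correctly. That power concerns efficacy only.

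**Step 4: size the infection component.**

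- Any infection = 1 − P(none). Prevena: 1 − 0.90 = 0.10, × 70 = 7. Dermabond: 1 − 0.70 = 0.30, × 70 = 21. Total 28.
- Grade III only. Prevena: 0.001 × 70 = 0.07. Dermabond: 0.03 × 70 = 2.1. Total 2.17.
- Ratio of totals: 28 / 2.17 ≈ 13.
- Chance of no Grade III infection in all 140: 0.999^70 × 0.97^70 = 0.11.

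**Step 5: add death, as illustration only.** The documents give no mortality rate. Assume a common 30-day mortality d in both arms, independent of infection. Then Grade III or death = 1 − (1 − d)(1 − P(III)).

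| d | Prevena | Dermabond |
|---|---|---|
| 0% | 0.1% | 3.0% |
| 2% | 2.1% | 4.9% |
| 5% | 5.1% | 7.9% |

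The any-infection reading stays at 10% v 30%, because the synopsis does not count deaths. Malfunction cannot be added, since no rate is given.

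**The case against.** **The synopsis is shorthand.** It names no grade, and the groin incision infection row in 8.2 can be read as defining its term as Grade III. Section 8.1 supports this: any wound infection already counts against the effectiveness endpoint, so an any-grade safety endpoint would largely repeat it. This stands as far as it goes. A reader might infer that the synopsis expressly counts infection of every grade; it does not say so. Even on the Grade III reading, however, it leaves out death and malfunction.

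**Table 2 lists adverse events, so harmless malfunctions naturally drop out.** This also stands in part, and it narrows the gap between 8.2 and Table 2. What remains is a malfunction that causes an adverse event short of Grade III infection or death: it counts under 8.2 and not under Table 2. Whether harmless malfunctions enter the 8.2 rate is still unstated. The MAE and SAE criteria list, which gives "Grade III Sziglgyi infection of the randomized incision" and also omits malfunction, adds little, because it omits death too and so is not a complete list of MAE components.

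**The fistula wording is obvious carry-over.** Agreed. It is a clean-up item and not a serious rival definition.

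**Every version could be computed from the data collected.** Szilagyi grade is assessed at each visit, and deaths and malfunctions are reported to the sponsor. That limits the harm. It does not say which version is the primary safety result.

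**Conclusion.** The inconsistency is real and should be corrected. It affects the reported primary safety rate and its interpretation; no safety test, alpha or power depends on it.

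Its size depends on how the synopsis is read. If it means any infection, the infection component is 10% v 30%, against 0.1% v 3% for Grade III only, using efficacy planning assumptions. If it means Grade III, the differences are death and malfunction, for which the documents give no rates.

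Three stronger readings are not supported:

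- **A single headline multiple between definitions.** For example, 0.10 / 0.001 = 100 for Prevena needs both the any-grade inference and no deaths.
- **Malfunctions will mask or create a difference between arms.** No malfunction rate is given and no between-arm safety comparison is planned. The documents show only that, on the Section 32.0 definition, one arm alone can score this component.
- **No governing rule exists anywhere.** That can be said only of the visible text, since some passages were removed before review.

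**What to change.** Issue a written amendment under Section 31.1, made before any review of outcomes by arm. An interim look is planned at half enrolment, and this revision (August 11, 2017) postdates the completion date projected in Section 7.3 (05/31/17). The amendment should therefore state whether results by arm have already been seen.

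1. Reconcile the synopsis, Section 8.2, Table 2 and Section 32.0 to one definition, and say that it governs. The natural core is what 8.2 and Table 2 already share: Grade III infection of the randomized incision *or* death from any cause, joined by *or* throughout.
2. State whether malfunction is a component and, if so, whether malfunctions without an adverse event count.
3. Because malfunction as defined can occur in one arm only, report the between-arm rate without it and list Prevena malfunctions separately.
4. Delete the AV-fistula definition.

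The cost is one amendment and a sponsor decision; the sample size is unchanged. The downside is imprecision. With 0.07 v 2.1 Grade III infections expected of 70 per arm, plus an unknown number of deaths, few events are likely. An any-grade definition would give more events but would largely duplicate the primary infection endpoint.

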1.0 Introduction

1.1 Objective:

The purpose of this study is to evaluate the efficacy and cost of Prevena versus Dermabond in the prevention of groin wound infections in patient who undergo vascular surgery which requires groin incision.

1.1a Device Name:

Prevena Incision Management System by Acelity

1.1b Intended Use: Prevena Incision Management System is a negative pressure wound therapy device that maintains a closed environment over the surgical incision and removes exudate through use of negative pressure. It is intended to be used on surgical incisions that continue to drain following closure with sutures or staples to prevent infection and promote healing.

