Class IV	Frequently bed or chair ridden for most of the day and is too weak and short of breath to do simple activities

Death: Termination of Life

Device Malfunction: Defined as a malfunction in the Prevena Incision Management System such that it did not perform its intended function when used in accordance with the *Instructions for Use*.

Device-Relatedness Categories of Adverse Events:

Device Related Adverse Event	AE that have a strong temporal relationship to the presence or performance of the device/system and an alternative etiology is highly unlikely
Probably Device Related Adverse Event	AE that have a strong temporal relationship to the presence or performance of the device/system and an alternative etiology is less likely than the potential relationship to the device/system
Probably–Not Device Related Adverse Event	AE that have minimal or no temporal relationship to the presence or performance of the device/system and/or a more than likely alternative etiology exists
Not Procedure –Related Adverse Event	AE is due to the underlying disease state or concomitant medication or therapy and not caused by the device/system

Device Success: Ability to deploy the Prevena Incision Management System as intended at the treatment site.

Diabetes (History of): Defined as subjects who have been diagnosed with either Type I or Type II diabetes and are currently diet controlled, taking oral hypoglycemic or insulin.

Discharge: The time-point in which the subject is released from the admitting hospital, transferred to another facility or expired.

Dissection: Intimal disruption of the vessel wall.

Embolus/Embolization: Obstruction of a blood vessel by a foreign substance (air, plaque debris or blood clot).

Emergent Surgical Revascularization: Surgery performed on an urgent or emergent basis.

Enrollment: The subject is enrolled after he/she has signed the informed consent and has been determined to meet all the inclusion criteria and no exclusion criteria.

Fever: An increase in internal body temperature to levels above normal: (37° C or 98.6° F).

Hematoma: Localized mass of extravasated blood.

Hemorrhage: Bleeding requiring hospitalization, repeat procedure, operation or Transfusion.

Hypertension: Increase in the systolic blood pressure over 140 mm Hg or a diastolic blood pressure above 90 mm Hg.

Hypotension: Fall in systolic blood pressure that requires treatment with vasopressors, inotropic agents or fluid resuscitation.

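### The section 8.2 primary safety composite includes device malfunction, which is defined only for Prevena and need not involve harm, so the arms are not compared on the same events

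*Combined protocol and SAP*

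**What the plan says.** Section 8.2 makes the primary safety endpoint a "major adverse event rate at 30 days defined as: device malfunction, Grade III Szilagyi Infection or any cause mortality". The three components differ in reach. Section 8.2 defines death with reference to both products, and infection by the randomized groin incision, so both can occur in either arm. Malfunction is different. Section 32.0 gives it as "Defined as a malfunction in the Prevena Incision Management System such that it did not perform its intended function". Section 8.2 speaks only of the device, but adds "The malfunctioned device will be returned to Acelity", and section 1.1a names the maker's product: "Prevena Incision Management System by Acelity". Section 9.4 gives a different manufacturer for Dermabond. No corresponding event is defined for Dermabond.

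On harmless faults, section 8.2 says: "Malfunctions that do not result in an adverse event do not need to be recorded as an adverse event".

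Three other places define the same endpoint, none with malfunction:

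- Table 2 (sections 11.4 to 11.11): "A primary safety endpoint adverse event defined as Szilagyi Grade III infection of the randomized incision and all-cause mortality".
- Synopsis: "Major adverse event rate at 30 days defined as: groin wound infection".
- Section 32.0, adverse event definitions: "A primary safety endpoint adverse event defined as thrombosis of the AV fistula, fistula re-intervention and all-cause mortality".

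**The concern.** A between-arm safety rate is interpretable when every component can happen in both arms and represents harm. The 8.2 composite fails the first condition, because only Prevena patients can have a malfunction as section 32.0 defines it. It may fail the second, because 8.2 lists malfunction with no requirement of harm while saying that a harmless malfunction is not an adverse event. Such a fault could then carry the same weight as a death or a graft infection, in one arm only.

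Grade III infection is expected to be rare, so a handful of one-arm events could decide which product appears to have the higher major adverse event rate.

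**Working it through.** **Inputs from the documents.** 70 patients per arm (section 4.1). Planning probabilities for none, grade I, II and III (section 9.13): Prevena 0.90, 0.08, 0.019, 0.001; Dermabond 0.70, 0.16, 0.11, 0.03.

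**Inputs that are assumptions.** The documents give neither a malfunction rate nor a 30-day mortality. Malfunction is taken as a count of 0, 2 or 3 patients, or as a rate up to 10%. Mortality is taken as equal in both arms, at 0%, 2% or 5%.

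**The plan's own figure.** There is no stated power or sample size for safety. The stated power of 0.88 belongs to the ordinal infection endpoint. Simulating 4,000 trials from the two vectors (two-sided 0.05, unstratified) gives 0.884 with the proportional-odds score test and 0.889 with the likelihood-ratio test. The grade III rates used below therefore come from a set of planning values that reproduces the plan's power.

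**Expected events without malfunction, no deaths.** Prevena 70 × 0.001 = 0.07; Dermabond 70 × 0.03 = 2.10; gap 2.03 in favour of Prevena.

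**Adding harmless malfunctions** in Prevena patients who have no other event:

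- two: 0.07 + 2 = 2.07 against 2.10, a tie in expectation;
- three: 0.07 + 3 = 3.07 against 2.10, a reversal.

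**Break-even rate.** If q is the malfunction rate and components are independent, the arms are equal when 1 − 0.999 × (1 − q) = 0.03, so q = 1 − 0.97/0.999 = 0.029, or about 2 of 70. Equal mortality multiplies both event-free probabilities by the same factor and cancels. For illustration, without deaths, q = 5% gives 70 × (1 − 0.999 × 0.95) = 3.57 Prevena events and q = 10% gives 70 × (1 − 0.999 × 0.90) = 7.06, each against 2.10.

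**Allowing for deaths and chance.** Expected events without malfunction are 70 × [1 − (1 − grade III rate) × (1 − mortality)]. The probabilities are exact binomial.

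| Mortality, both arms | Expected events without malfunction, Prevena vs Dermabond | Chance that Prevena shows more events with 0 / 2 / 3 harmless malfunctions |
|---|---|---|
| 0% | 0.07 vs 2.10 | 0.009 / 0.39 / 0.66 |
| 2% | 1.47 vs 3.46 | 0.12 / 0.42 / 0.61 |
| 5% | 3.57 vs 5.50 | 0.20 / 0.44 / 0.58 |

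With malfunction left out, the expected gap stays near 2 events (2.03, 1.99 and 1.93), and Prevena has fewer events with probability 0.86, 0.75 and 0.69.

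**Significance.** Fisher's exact test gives p = 0.50 for 0 vs 2 events and p = 1.0 for 3 vs 2. Against 2 Dermabond events, 9 Prevena events give p = 0.055 and 10 give p = 0.031.

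**The case against.** The strongest reply is that 8.2 can be read so that only harmful malfunctions count: the endpoint is an adverse event rate, and the same section excludes harmless malfunctions from adverse events. That reading is fair, and on it the count of harmless faults falls away. But 8.2 does not state it, and even then the component could occur only in the Prevena arm.

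A second reply is that the real defect is inconsistent definitions, since Table 2 already omits malfunction, as does the table of criteria for major and serious events after Table 3. This stands in part: it is unsettled whether malfunction counts at all, so bias is not certain. But aligning everything to 8.2 would keep the asymmetry, so the direction of the reconciliation matters.

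Third, equal weighting of unequal components is common in composites, and any tilt here runs against the sponsor's own product. Neither makes a rate with a one-arm component easier to interpret.

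Three stronger conclusions are tempting, and the documents do not support them.

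- A reader might infer that two or three faults would overturn a safety finding. The analysis outlines in 9.12 and section 11 cover infection grade and cost, and the interim text names a test only for infection rates. There is no planned safety test to overturn.
- A reader might infer that two faults are enough to reverse the direction. In expectation two only tie the arms; they reverse the order only when Dermabond happens to have fewer events relative to Prevena than planned.
- A reader might infer that Dermabond failures go unseen. Failure to heal counts in the 8.1 effectiveness endpoint in both arms, adverse events are collected whatever the product (9.2, Table 2), and unscheduled visits for the randomized incision are recorded (9.5).

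**Conclusion.** The point holds as a defect of definition. The 8.2 composite has one component that only Prevena patients can experience, does not say whether harmless faults count, and disagrees with Table 2 on the same endpoint.

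Its size is modest in absolute terms but comparable to the signal: the expected difference is about 2 events, and a Prevena malfunction rate of about 2.9% cancels it. This rests on the plan's grade III rates, equal mortality, and the reading under which harmless malfunctions count. The malfunction rates are assumptions. What can change is the observed direction of small counts, not a significance result. The asymmetry itself depends on none of these figures.

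It should be corrected, because this is a primary safety endpoint, but it does not touch the powered infection analysis.

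**What to change.** Remove device malfunction from the 8.2 composite, so that the endpoint is grade III infection of the randomized incision or death from any cause, with either event counting, as in Table 2. Reconcile the synopsis and the section 32.0 major adverse event entry with that definition.

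Report device or product deficiencies separately by arm, with a definition that covers Dermabond as well as Prevena, and state for each whether it led to an adverse event. A malfunction that causes a grade III infection or a death still enters the composite through that harm; other resulting harms remain adverse events.

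The cost is wording in the synopsis, 8.2 and section 32.0, and one case report form line for Dermabond deficiencies. Sample size, the primary analysis and the reporting of malfunctions to the sponsor are unchanged.
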